7.3. Variables

The described variables are classified into two variable groups according to the role, the clinical outcome and baseline (demographic, clinical, treatment variables). The latter include the possible subgroups to consider. These analyses are initially exploratory to the extent that the specific analyses may be performed according to the sample collected.

Table 1. Table of Variables

Variable	Role	Data source (s)	Operational definition
Age	Demographic characteristic	Medical record	Birthday
Gender	Demographic characteristic	Medical record	Male, female, other
Race	Demographic characteristic	Medical record	White, half-breed, indigenous, black, others
Weight	Demographic characteristic	Medical record	Kg
Height	Demographic characteristic	Medical record	Mt (meters)
Body mass index	Demographic characteristic	Medical record	Kg/mt ²
City of residence	Demographic characteristic	Medical record	Cities of Colombia
Time to diagnosis to NVAF	Clinical characteristic	Medical record	Date (dd/mm/yy)
High alcohol intake at OAC prescription date	Clinical characteristic	Medical record	Yes, No

Variable	Role	Data source (s)	Operational definition
Diabetes	Clinical characteristic	Medical record	No, without chronic complication, with end-organ damage
Liver disease	Clinical characteristic	Medical record	No, mild, moderate, severe
Hypertension	Clinical characteristic	Medical record	Diagnosis of hypertension (Yes, No)
Uncontrolled hypertension at OAC prescription date	Clinical characteristic	Medical record	Yes, No
Rheumatic disease	Clinical characteristic	Medical record	Yes, No
Acquired Immune Deficiency Syndrome (AIDS)	Clinical characteristic	Medical record	Yes, No
Severe renal disease (dialysis, organ transplant)	Clinical characteristic	Medical record	Yes, No
Moderate renal disease (creatinine > 3 mg/dL)	Clinical characteristic	Medical record	Yes, No
Chronic heart failure	Clinical characteristic	Medical record	Yes, No
Myocardial infarction	Clinical characteristic	Medical record	Yes, No
Chronic obstructive pulmonary disease (COPD)	Clinical characteristic	Medical record	Yes, No
Peripheral vascular disease	Clinical characteristic	Medical record	Yes, No
Stroke or transient ischemic attack (TIA)	Clinical characteristic	Medical record	Yes, No
Dementia	Clinical characteristic	Medical record	Yes, No
Hemiplegia	Clinical characteristic	Medical record	Yes, No
Connective tissue disease	Clinical characteristic	Medical record	Yes, No

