I130	Hypertensive heart and renal disease with (congestive) heart failure
I132	Hypertensive heart and renal disease with both (congestive) heart failure and renal failure
I110	Hypertensive heart disease with (congestive) heart failure

- *Peripheral vascular disease*

ICD-10	Description
I70	Atherosclerosis
I71	Aortic aneurysm and dissection
I731	Thromboangiitis obliterans [Buerger]
I738	Other specified peripheral vascular diseases
I739	Peripheral vascular disease, unspecified

PFIZER CONFIDENTIAL

ICD-10	Description
I771	Stricture of artery
I790	Aneurysm of aorta in diseases classified elsewhere
I792	Peripheral angiopathy in diseases classified elsewhere
K551	Chronic vascular disorders of intestine
K558	Other vascular disorders of intestine
K559	Vascular disorder of intestine, unspecified
Z958	Presence of other cardiac and vascular implants and grafts
Z959	Presence of cardiac and vascular implant and graft, unspecified

▪ *Dementia*

ICD-10	Description
F00	Dementia in Alzheimer's disease
F01	Vascular dementia
F02	Dementia in other diseases classified elsewhere
F03	Unspecified dementia
G30	Alzheimer's disease
F051	Delirium superimposed on dementia
G311	Senile degeneration of brain, not elsewhere classified

▪ *Cerebrovascular disease*

ICD-10	Description
G45	Transient cerebral ischaemic attacks and related syndromes
G46	Vascular syndromes of brain in cerebrovascular diseases
I60	Subarachnoid haemorrhage
I61	Intracerebral haemorrhage
I62	Other nontraumatic intracranial haemorrhage
I63	Cerebral infarction
I64	Stroke, not specified as haemorrhage or infarction
I65	Occlusion and stenosis of precerebral arteries, not resulting in cerebral infarction
I66	Occlusion and stenosis of cerebral arteries, not resulting in cerebral infarction
I67	Other cerebrovascular diseases
I68	Cerebrovascular disorders in diseases classified elsewhere
I69	Sequelae of cerebrovascular disease
H340	Transient retinal artery occlusion

▪ *Chronic pulmonary disease*

ICD-10	Description
J40	Bronchitis, not specified as acute or chronic
J41	Simple and mucopurulent chronic bronchitis
J42	Unspecified chronic bronchitis
J43	Emphysema
J44	Other chronic obstructive pulmonary disease
J45	Asthma
J46	Status asthmaticus
J47	Bronchiectasis
J60	Coalworker's pneumoconiosis
J61	Pneumoconiosis due to asbestos and other mineral fibres
J62	Pneumoconiosis due to dust containing silica

PFIZER CONFIDENTIAL

ICD-10	Description
J63	Pneumoconiosis due to other inorganic dusts
J64	Unspecified pneumoconiosis

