E121	Malnutrition-related diabetes mellitus with ketoacidosis
E126	Malnutrition-related diabetes mellitus with other specified complications
E128	Malnutrition-related diabetes mellitus with unspecified complications
E129	Malnutrition-related diabetes mellitus without complications

PFIZER CONFIDENTIAL

ICD-10	Description
E130	Other specified diabetes mellitus with coma
E131	Other specified diabetes mellitus with ketoacidosis
E136	Other specified diabetes mellitus with other specified complications
E138	Other specified diabetes mellitus with unspecified complications
E139	Other specified diabetes mellitus without complications
E140	Unspecified diabetes mellitus with coma
E141	Unspecified diabetes mellitus with ketoacidosis
E146	Unspecified diabetes mellitus with other specified complications
E148	Unspecified diabetes mellitus with unspecified complications
E149	Unspecified diabetes mellitus without complications

2 point each:

▪ *Hemiplegia or paraplegia*

ICD-10	Description
G81	Hemiplegia
G82	Paraplegia and tetraplegia
G041	Tropical spastic paraplegia
G114	Hereditary spastic paraplegia
G801	Spastic diplegia
G802	Infantile hemiplegia
G830	Diplegia of upper limbs
G831	Monoplegia of lower limb
G832	Monoplegia of upper limb
G833	Monoplegia, unspecified
G834	Cauda equina syndrome
G839	Paralytic syndrome, unspecified
G81	Hemiplegia
G82	Paraplegia and tetraplegia
G041	Tropical spastic paraplegia
G114	Hereditary spastic paraplegia
G801	Spastic diplegia
G802	Infantile hemiplegia
G830	Diplegia of upper limbs
G831	Monoplegia of lower limb
G832	Monoplegia of upper limb
G833	Monoplegia, unspecified
G834	Cauda equina syndrome
G839	Paralytic syndrome, unspecified

▪ *Moderate or severe renal disease*

ICD-10	Description
N18	Chronic renal failure
N19	Unspecified renal failure
N052	Diffuse membranous glomerulonephritis
N053	Diffuse mesangial proliferative glomerulonephritis
N054	Diffuse endocapillary proliferative glomerulonephritis
N055	Diffuse mesangiocapillary glomerulonephritis
N056	Dense deposit disease
N057	Diffuse crescentic glomerulonephritis

PFIZER CONFIDENTIAL

ICD-10	Description
N250	Renal osteodystrophy
I120	Hypertensive renal disease with renal failure
I131	Hypertensive heart and renal disease with renal failure
N032	Diffuse membranous glomerulonephritis
N033	Diffuse mesangial proliferative glomerulonephritis
N034	Diffuse endocapillary proliferative glomerulonephritis
N035	Diffuse mesangiocapillary glomerulonephritis
N036	Dense deposit disease

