H: I10, I11, I12, I13, I15

Score 1 point

ICD-10	Description
I10	Essential (primary) hypertension
I11	Hypertensive heart disease
I12	Hypertensive renal disease
I13	Hypertensive heart and renal disease
I15	Secondary hypertension

A: Age \geq 75 years

Score 2 points

D: E10 a E14

Score 1 point

ICD-10	Description
E10	Insulin-dependent diabetes mellitus
E11	Non-insulin-dependent diabetes mellitus
E12	Malnutrition-related diabetes mellitus
E13	Other specified diabetes mellitus
E14	Unspecified diabetes mellitus

S2: G45.0, G45.1, G45.2, G45.3, G45.8, G45.9

Score 2 points

ICD-10	Description
G450	Vertebral-basilar artery syndrome
G451	Carotid artery syndrome (hemispheric)
G452	Multiple and bilateral precerebral artery syndromes
G453	Amaurosis fugax
G458	Other transient cerebral ischaemic attacks and related syndromes

V: I26, I82, I21- I25, I65, I70- I72, I73.1, I73.8, I73.9, I79.0, I79.2, K55.1, K55.8, K55.9, Z95.8, Z95.9

Score 1 point

ICD-10	Description
I26	Pulmonary embolism
I82	Other venous embolism and thrombosis
I21	Acute myocardial infarction
I22	Subsequent myocardial infarction
I23	Certain current complications following acute myocardial infarction
I24	Other acute ischaemic heart diseases
I25	Chronic ischaemic heart disease
I65	Occlusion and stenosis of precerebral arteries, not resulting in cerebral infarction
I70	Atherosclerosis
I71	Aortic aneurysm and dissection
I72	Other aneurysm
I731	Thromboangiitis obliterans [Buerger]
I738	Other specified peripheral vascular diseases
I739	Peripheral vascular disease, unspecified
I790	Aneurysm of aorta in diseases classified elsewhere
I792	Peripheral angiopathy in diseases classified elsewhere
K551	Chronic vascular disorders of intestine
K558	Other vascular disorders of intestine

A: Age 64-74 years

Score 1 point

Sc: Sex category (female)

Score 1

- **HASBLED score:** The HAS-BLED score will be used to analyze the risk of bleeding. The modified HAS-BLED score ranges from 0 to 8. ICD-10 diagnostic codes for each component of the index when applicable:

•

H: I10, I11, I12, I13, I15

Score 1 point

ICD-10	Description
I10	Essential (primary) hypertension
I11	Hypertensive heart disease
I12	Hypertensive renal disease
I13	Hypertensive heart and renal disease
I15	Secondary hypertension

Apixaban

B0661148- NON-INTERVENTIONAL STUDY PROTOCOL

Final, 10 October 2019

A: N03.2, N03.3, N03.4, N03.5, N03.6, N03.7, N05.2, N05.3, N05.4, N05.5, N05.6, N057, N18- N19, N25.0, Z49.0, Z49.2, Z94.0, Z99.2

Score 1 point

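### The Charlson renal code list omits I13.2, the HAS-BLED renal list omits four renal codes, and Table 1 uses the same severity terms for a different variable

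*Combined protocol and SAP*

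**What the plan says.** Section 7.3.1, under the covariate definitions, builds the Charlson index from listed ICD-10 codes and fixed points.

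- **Charlson renal item (2 points), "Moderate or severe renal disease".** The list has 22 distinct codes. It takes N18 ("Chronic renal failure") and N19 ("Unspecified renal failure") as whole categories, with no stage or creatinine condition. It also takes I12.0, I13.1 ("Hypertensive heart and renal disease with renal failure"), glomerulonephritis codes, N25.0, and dialysis and kidney transplant codes including Z49.1. I13.2 is not in it.
- **Charlson heart failure item (1 point).** This list contains I13.2, described as "Hypertensive heart and renal disease with both (congestive) heart failure and renal failure".
- **HAS-BLED renal item A (1 point).** After the glomerulonephritis codes the list ends "N18- N19, N25.0, Z49.0, Z49.2, Z94.0, Z99.2". It has no I12.0, I13.1, I13.2 or Z49.1.
- **Table 1 (Section 7.3).** Two Yes/No fields are taken from the medical record: "Moderate renal disease (creatinine > 3 mg/dL" and "Severe renal disease (dialysis, organ transplant". (The closing bracket is left off both quotes.)

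No section says how the Table 1 fields relate to the Charlson renal item.

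**The concern.** I13.2 describes a patient with renal failure and heart failure together. The Charlson list credits I13.1, the neighbouring code with renal failure, as renal disease but not I13.2, so the patient described as having both conditions scores lower than the patient described as having renal failure. That is an omission from a list, since the plan gives no reason for treating the two codes differently.

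The HAS-BLED list has a wider gap. Four codes that the protocol describes as renal failure or dialysis earn no renal point there, and three of the four count as renal disease in the Charlson index. The same patient can be a renal patient in one score and not in the other.

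The third issue is one of reading. Table 1 and the Charlson index share the terms moderate and severe renal disease but measure different things. Describing clinical characteristics is a primary objective (Section 6), so a reader of the report may take two different figures for the same variable.

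**Working it through.** The plan states no figure on this point, so there is none to reproduce. The check enters the lists as printed, scores patients who carry a single code, and compares.

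**Charlson, heart failure and renal items only** (points = 1 × heart failure + 2 × renal; age and other items left out):

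| Only code carried | As written | With I13.2 added to the renal list |
|---|---|---|
| I13.2 | 1 + 0 = 1 | 1 + 2 = 3 |
| I13.1 | 0 + 2 = 2 | 2 |
| I12.0 | 0 + 2 = 2 | 2 |
| any N18 code | 0 + 2 = 2 | 2 |
| N19 | 0 + 2 = 2 | 2 |

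The shortfall for I13.2 is 3 − 1 = 2 points. No other code changes.

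**HAS-BLED renal list against the Charlson renal list.** The codes in Charlson but not in HAS-BLED are I12.0, I13.1 and Z49.1. No code is in HAS-BLED but not in Charlson. I13.2 is in neither.

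HAS-BLED item H lists I12 and I13 as whole categories, so hypertension plus renal points for single-code patients are:

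| Only code carried | As written | With the four codes added |
|---|---|---|
| I12.0, I13.1 or I13.2 | 1 + 0 = 1 | 1 + 1 = 2 |
| Z49.1 | 0 + 0 = 0 | 0 + 1 = 1 |

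The shortfall is 1 point in each case.

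**May one code count under two items?** The protocol already allows it. In CHA2DS2-VASc, I13.2 is listed under C, and all of I13 under H. In HAS-BLED, K76.2 is listed under both the liver item and the bleeding item. Counting I13.2 under both heart failure and renal disease in Charlson follows that practice.

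**Table 1 against the Charlson codes.** The two can disagree in both directions:

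- N18 or N19 coded, creatinine at or below 3 mg/dL, no dialysis or transplant: No on both Table 1 fields, 2 Charlson points.
- Creatinine above 3 mg/dL in the chart, no listed renal code: Yes in Table 1, 0 Charlson renal points.

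The documents give no code frequencies and no creatinine distribution, so neither group can be sized and the net direction is unknown. Table 2 does not settle the matter: as its text reads, the row labelled renal disease lists hepatitis and other liver codes.

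**The case against.** The strongest reply is that little depends on this. Only patients with no other listed renal code are under-scored; anyone with I13.2 who also carries N18, N19 or a dialysis code gets the renal points anyway. I13.2 is not ignored either: it earns the Charlson heart failure point and counts under hypertension in both CHA2DS2-VASc and HAS-BLED. Section 7.7 names no analysis that uses the Charlson index, and no comparison between treatments is planned. Cohort assignment, persistence, stroke or systemic embolism, and bleeding are untouched. All of this stands. It limits the size of the point but does not make the lists consistent.

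A reader might go further and infer three things that the documents do not support.

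- **That Charlson is inflated because N18 and N19 carry no severity condition.** This takes the Table 1 threshold as the standard for Charlson. Section 7.3.1 builds the index from codes, and nothing says that the Table 1 fields feed it. Table 1 does follow the Charlson items closely (graded diabetes and liver disease, hemiplegia, AIDS, metastatic tumor), so the overlap needs explaining, but no stated rule is broken.
- **That HAS-BLED is inflated in the same way.** Its item A concerns abnormal renal function, as the abbreviation list shows, and is not limited to moderate or severe disease. Giving a point for N18 or N19 contradicts nothing.
- **That the index should be scored from the chart, with codes used where the chart is silent.** A patient coded N18 with creatinine below the threshold would then score 0 if the chart field were filled and 2 if it were empty. That mixes two definitions in one score and sits badly with Section 7.7.1, which rules out replacing missing data.

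**Conclusion.** The point holds as a code-list error with a labelling ambiguity beside it. A patient whose only renal code is I13.2 gets 1 Charlson point from the heart failure and renal items, against 2 for I13.1 alone and 3 if both conditions were counted. In HAS-BLED, a patient whose only renal code is I12.0, I13.1, I13.2 or Z49.1 gets no renal point, which is 1 too few by the protocol's own descriptions of those codes.

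This rests on two assumptions: that the printed descriptions mean what they say, and that one code may count under two items, as the protocol allows elsewhere. The consequence is limited to descriptive baseline scores. The number of patients affected, and any shift in mean scores, cannot be computed from the documents. The shared wording of Table 1 and Charlson is an unreconciled pair of definitions; it does not show that either score is too high.

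**What to change.** 1. In Section 7.3.1, add I13.2 to the Charlson renal list and keep it under heart failure.
2. Add I12.0, I13.1, I13.2 and Z49.1 to the HAS-BLED renal list, in both the code string and the table below it. Adding I13.2 alone would leave HAS-BLED counting it but not I12.0 or I13.1.
3. Keep the Charlson renal item code-based, label it in the tables as code-defined renal disease, and report the two Table 1 chart fields beside it with a footnote saying that they are a different variable.

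The cost is a few entries in two lists, one label and one footnote. No new data are needed: the Charlson index as written already uses all four codes, I13.2 for heart failure and the other three for renal disease. The two renal measures will still give different figures, but the report will say why.

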8.4 Ethical Conduct of the Study.....	49
9 MANAGEMENT AND REPORTING OF ADVERSE EVENTS/ADVERSE REACTIONS	50
10 PLANS FOR DISSEMINATING AND COMMUNICATING STUDY RESULTS	51
11. REFERENCES	52
12. LIST OF TABLES	53
13. LIST OF FIGURES	53
ANNEX 1. LIST OF STAND ALONE DOCUMENTS	53
ANNEX 2. ENCEPP CHECKLIST FOR STUDY PROTOCOLS	53

PFIZER CONFIDENTIAL

LIST OF ABBREVIATIONS

Abbreviation	Definition
ARB	Angiotensin II receptor blockers
ACE	Angiotensin-converting-enzyme inhibitor
AE	Adverse event
AEM	Adverse event monitoring
AIDS	Acquired Immune Deficiency Syndrome
AF	Atrial fibrillation
ANOVA	Analysis of variance
ATC	Anatomical Therapeutic Chemical
CHA ₂ DS ₂ -VASc	C: Congestive heart failure
	H: Hypertension
	A: Age \geq 75 years
	D: Diabetes mellitus
	S ₂ : Prior Stroke or transient ischemic attack or Thromboembolism
	V: Vascular disease (peripheral artery disease, myocardial infarction, aortic plaque)
	A: Age 65–74 years
	Sc: Sex category (female sex)
CHADS ₂	C: Congestive heart failure
	H: Hypertension
	A: Age \geq 75 years
	D: Diabetes mellitus
	S ₂ : Prior Stroke or transient ischemic attack or Thromboembolism
COPD	Chronic obstructive pulmonary disease
ECR	Electronic Case Report
GEP	Good Epidemiological Practice
GPP	Good Pharmacoepidemiology Practices
HAS-BLED	H: Hypertension
	A: Abnormal renal and liver function
	S: Stroke
	B: Bleeding
	L: Labile INR
	E: Elderly
	D: Drugs or alcohol
HMO	Health Maintenance Organizations
ICD-10	10th revision of the International classification of diseases
IEA	International Epidemiological Association
IEC	Independent Ethics Committee
INR	International normalized ratio
IRB	Institutional Review Board
ISPE	International Society for Pharmacoepidemiology
ISPOR	International Society for Pharmacoeconomics and Outcomes Research
MANOVA	Multivariate analysis of variance
NI	Non- interventional
NIS	Non-interventional study
NOAC	New oral anticoagulant
NSAID	Non-steroidal anti-inflammatory drugs
NVAF	Non-valvular atrial fibrillation

PFIZER CONFIDENTIAL

Apixaban
B0661148- NON-INTERVENTIONAL STUDY PROTOCOL
Final, 10 October 2019

Abbreviation	Definition
OAC	Oral anticoagulant
SAMe-TT ₂ R ₂	S: Sex (female)
	A: Age (<60 years)
	Me: Medical history
	T: Treatment
	T: Tobacco use (within 2 years)
	R: Race (non-Caucasian)
SPSS	Statistical Package for the Social Sciences
TIA	Transient ischaemic attack
VKA	Vitamin K Antagonist
VTE	Venous thromboembolism

PFIZER CONFIDENTIAL

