K272	Acute with both haemorrhage and perforation
K274	Chronic or unspecified with haemorrhage
K276	Chronic or unspecified with both haemorrhage and perforation
K280	Acute with haemorrhage
K282	Acute with both haemorrhage and perforation
K284	Chronic or unspecified with haemorrhage
K286	Chronic or unspecified with both haemorrhage and perforation
K290	Acute haemorrhagic gastritis
K625	Haemorrhage of anus and rectum
K920	Haematemesis
K921	Melaena
K922	Gastro-intestinal haemorrhage, unspecified
D62	Acute posthaemorrhagic anaemia
H356	Retinal haemorrhage
H431	Vitreous haemorrhage
H450	Vitreous haemorrhage in diseases classified elsewhere
H922	Otorrhagia
I312	Haemopericardium, not elsewhere classified
J942	Haemothorax
R04	Haemorrhage from respiratory passages
K661	Haemoperitoneum
M250	Haemarthrosis
N02	Recurrent and persistent haematuria
N938	Other specified abnormal uterine and vaginal bleeding
N939	Abnormal uterine and vaginal bleeding, unspecified
N950	Postmenopausal bleeding
R31	Unspecified haematuria
R58	Haemorrhage, not elsewhere classified
T792	Traumatic secondary and recurrent haemorrhage

- Ischemic stroke:** Patients who report the following diagnoses in the medical history during the follow-up period:

ICD-10	Description
I63	Cerebral infarction
I64	Stroke, not specified as haemorrhage or infarction

Except I63.6 Cerebral infarction due to thrombosis of cerebral veins, non-pyogenic

- Hemorrhagic stroke:** Patients presenting the following diagnosis in the medical record:

PFIZER CONFIDENTIAL

ICD-10	Description
I60	Subarachnoid haemorrhage
I61	Intracerebral haemorrhage
I62	Other nontraumatic intracranial haemorrhage

- **Systemic embolism:** Patients who report any of the following diagnoses:

ICD-10	Description
I74	Arterial embolism and thrombosis

Definition of covariates

- **Age:** Categorical variable, continues in years. It will be defined from the index date and will be used to assign patients to the following age categories:

18 - 49
 50 - 59
 60 - 69
 70 - 79
 ≥ 80 years old.

- **Charlson Index:** Charlson comorbidity index will be created during the reference period taking into account the following score:

1 point each:

- *Myocardial infarction*

ICD-10	Description
I21	Acute myocardial infarction
I22	Subsequent myocardial infarction
I252	Old myocardial infarction

- *Congestive heart failure*

ICD-10	Description
I110	Hypertensive heart disease with (congestive) heart failure

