ICD-10	Description
N032	Diffuse membranous glomerulonephritis
N033	Diffuse mesangial proliferative glomerulonephritis
N034	Diffuse endocapillary proliferative glomerulonephritis
N035	Diffuse mesangiocapillary glomerulonephritis
N036	Dense deposit disease
N037	Diffuse crescentic glomerulonephritis
N052	Diffuse membranous glomerulonephritis
N053	Diffuse mesangial proliferative glomerulonephritis
N054	Diffuse endocapillary proliferative glomerulonephritis
N055	Diffuse mesangiocapillary glomerulonephritis
N056	Dense deposit disease
N057	Diffuse crescentic glomerulonephritis
N18	Chronic renal failure
N19	Unspecified renal failure
N250	Renal osteodystrophy
Z490	Preparatory care for dialysis
Z492	Other dialysis
Z940	Kidney transplant status
Z992	Dependence on renal dialysis

A: B18, I85, I86.4, I98.2, K70, K71.1, K71.3, K71.4, K71.5, K71.7, K72.1, K72.9, K73, K74, K76.0, K76.2, K76.3, K76.4, K76.5, K76.6, K76.7, K76.8, K76.9, Z94.4

Score 1 point

ICD-10	Description
B18	Chronic viral hepatitis
I85	Oesophageal varices
I864	Gastric varices
I982	Oesophageal varices in diseases classified elsewhere
K70	Alcoholic liver disease
K711	Toxic liver disease with hepatic necrosis
K713	Toxic liver disease with chronic persistent hepatitis
K714	Toxic liver disease with chronic lobular hepatitis
K715	Toxic liver disease with chronic active hepatitis
K717	Toxic liver disease with fibrosis and cirrhosis of liver
K721	Chronic hepatic failure
K729	Hepatic failure, unspecified
K73	Chronic hepatitis, not elsewhere classified
K74	Fibrosis and cirrhosis of liver
K760	Fatty (change of) liver, not elsewhere classified
K762	Central haemorrhagic necrosis of liver
K763	Infarction of liver
K764	Peliosis hepatis
K765	Hepatic veno-occlusive disease
K766	Portal hypertension
Z944	Liver transplant status

S: I64, I69.3, D62, D68.3, D69.8, D69.9, H31.3, H35.6, H43.1, H45.0, H92.2, I23.0, I31.2

Score 1 point

PFIZER CONFIDENTIAL

ICD-10	Description
I64	Stroke, not specified as haemorrhage or infarction
I693	Sequelae of cerebral infarction
D62	Acute posthaemorrhagic anaemia
D683	Haemorrhagic disorder due to circulating anticoagulants
D698	Other specified haemorrhagic conditions
D699	Haemorrhagic condition, unspecified
H313	Choroidal haemorrhage and rupture
H356	Retinal haemorrhage
H431	Vitreous haemorrhage
H450	Vitreous haemorrhage in diseases classified elsewhere
H922	Otorrhagia
I230	Haemopericardium as current complication following acute myocardial infarction

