Z714	Alcohol abuse counselling and surveillance
Z721	Alcohol use

Codes Anatomical Therapeutic Chemical (ATC): B01AC, M01A

- SMAe-TT₂R₂ score:** The estimation of SAMe-TT₂R₂ will be performed by adding the following variables:

Sex (female) Score 1 point

Age (<60 years) Score 1 point

Medical history (history of more than two of the following: hypertension, diabetes, coronary artery disease or myocardial infarctions, peripheral artery disease, heart failure, stroke; pulmonary, hepatic, or renal disease) Score 1 point

Treatment (interacting medications , amiodarone ATC- C01BD01) Score 1 point

Tobacco use (within 2 years) Score 2 points

PFIZER CONFIDENTIAL

Race (non-Caucasian) Score 2 points

Table 2. Baseline variables or possible confounders

Variable	Operacional definition ICD-10
Diabetes	E10 Insulin-dependent diabetes mellitus E11 Non-insulin-dependent diabetes mellitus E12 Malnutrition-related diabetes mellitus E13 Other specified diabetes mellitus E14 Unspecified diabetes mellitus
Hypertension	I10 Essential (primary) hypertension I11 Hypertensive heart disease I12 Hypertensive renal disease I13 Hypertensive heart and renal disease I15 Secondary hypertension
Ischaemic stroke	I63 Cerebral infarction Excepto I636 Cerebral infarction due to cerebral venous thrombosis, nonpyogenic I64 Stroke, not specified as haemorrhage or infarctionz
Haemorrhagic stroke	I60 Subarachnoid haemorrhage I61 Intracerebral haemorrhage I62 Other nontraumatic intracranial haemorrhage

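### The written code lists for CHA2DS2-VASc and HAS-BLED contradict the protocol's own component labels: prior stroke and embolism are mostly missing, bleeding codes sit under stroke, and one age band is off by a year

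*Combined protocol and SAP*

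**What the plan says.** Describing clinical characteristics is part of the first primary objective. Table 1 lists CHA2DS2-VASc and HAS-BLED at the start of anticoagulation as clinical characteristics, with the medical record as source. Section 7.3.1, under the covariate definitions, presents them as the measures of stroke risk and bleeding risk and gives ICD-10 codes for each component where codes apply.

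- CHA2DS2-VASc, two-point stroke component: "S2: G45.0, G45.1, G45.2, G45.3, G45.8, G45.9". The List of Abbreviations labels it "Prior Stroke or transient ischemic attack or Thromboembolism".
- HAS-BLED, one-point stroke component: "S: I64, I69.3, D62, D68.3, D69.8, D69.9, H31.3, H35.6, H43.1, H45.0, H92.2, I23.0, I31.2". The List of Abbreviations labels it simply as stroke.
- HAS-BLED bleeding component: a separate list that includes I60, I61, I62 and gastrointestinal codes such as K92.2.
- CHA2DS2-VASc, lower age component: 64-74 years in section 7.3.1, 65-74 years in the List of Abbreviations.

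The protocol's own stroke and embolism codes are given in section 7.3.1 and repeated in Table 2. Ischaemic stroke is I63 and I64, with a carve-out ("Except I63.6 Cerebral infarction due to thrombosis of cerebral veins, non-pyogenic"). Haemorrhagic stroke is "I60 Subarachnoid haemorrhage I61 Intracerebral haemorrhage I62 Other nontraumatic intracranial haemorrhage". Systemic embolism is I74, "Arterial embolism and thrombosis".

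**The concern.** A component labelled prior stroke, TIA or thromboembolism whose list contains only TIA-type codes does not measure what its label says. Patients with a past infarct or embolism would be placed too low on the stroke-risk scale, so the upper part of the reported distribution would be understated.

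The HAS-BLED stroke list fails in two ways. It misses cerebral infarction under its main code, and it gives a stroke point for bleeding diagnoses such as D62, "Acute posthaemorrhagic anaemia". The two scores also disagree with each other: I64 and I69.3 count as prior stroke in HAS-BLED but earn nothing in CHA2DS2-VASc. The same patient can therefore have a stroke history in one score and none in the other.

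At stake is the accuracy of two baseline descriptors under a primary objective, and of any subgroup later formed from them.

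**Working it through.** The plan gives no figure to reproduce, so the check compares code lists. The component code lines in the running text were used rather than the tables beneath them, because tables can lose rows in conversion to text.

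**Counts.** The CHA2DS2-VASc stroke line has 6 codes, all G45. The protocol's stroke and embolism codes are I60, I61, I62, I63, I64 and I74; 0 of these 6 are in that line. The HAS-BLED stroke line has 13 codes: 2 stroke codes (I64, I69.3) and 13 - 2 = 11 haemorrhage codes. Six of the 11 (D62, H35.6, H43.1, H45.0, H92.2, I31.2) are on the protocol's own major-bleeding list. The HAS-BLED stroke and bleeding lines share no code.

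**Points earned by each code under the printed lines.**

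| Code | CHA2DS2-VASc stroke | CHA2DS2-VASc vascular | HAS-BLED stroke | HAS-BLED bleeding |
|---|---|---|---|---|
| I60, I61, I62 | 0 | 0 | 0 | 1 |
| I63 | 0 | 0 | 0 | 0 |
| I64 | 0 | 0 | 1 | 0 |
| I69.3 | 0 | 0 | 1 | 0 |
| I74 | 0 | 0 | 0 | 0 |
| G45.9 | 2 | 0 | 0 | 0 |
| D62 | 0 | 0 | 1 | 0 |

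**Worked patient.** Woman aged 70, hypertension coded I10, prior infarct coded I63 (not I63.6), no G45 code, nothing else.

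- CHA2DS2-VASc by label: hypertension 1 + age 1 + sex 1 + stroke 2 = 5. By list: 1 + 1 + 1 + 0 = 3.
- HAS-BLED by label: hypertension 1 + age 1 + stroke 1 = 3. By list: 1 + 1 + 0 = 2.

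**The 11 haemorrhage codes.** Only the stroke and bleeding components are counted here.

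- K92.2 with D62, no stroke: by list, bleeding 1 + stroke 1 = 2. With D62 under bleeding: 1. The total is 1 too high.
- D62 alone: by list, stroke 1. With D62 under bleeding: bleeding 1. The total is unchanged; only the component is wrong.
- I64 with D62, no code from the bleeding line: by list, stroke 1. With D62 under bleeding: stroke 1 + bleeding 1 = 2. The total is 1 too low.

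**Age.** A 64-year-old scores 1 under the printed band and 0 under the labelled band.

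**Cohort scale, by assumption only.** The documents give no prevalence of prior stroke. Let p be the share of the 7,500 patients with a prior stroke or embolism and no G45 code, and suppose the list is applied to all of them. Then 7,500 × p patients are 2 points low, and the cohort mean falls by 2 × p. For an assumed p of 5%, that is 375 patients and 0.1 points; for 30%, it is 2,250 patients and 0.6 points.

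**The case against.** The strongest reply is that the scores will not be computed from these lists. Table 1 gives the medical record as the source of both scores and lists stroke, TIA, thromboembolism and bleeding histories as separate chart items. Section 7.6.1 has trained physicians do the abstraction. Section 7.3.1 offers the codes only where they apply, and the List of Abbreviations states the stroke components correctly. A physician scoring from the chart may never use the faulty lists.

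Much of this stands, and it limits what can be claimed. It does not remove the error. Table 1 names a source, not a scoring rule, and no text links the chart histories to the score components or says which governs. Section 7.6.1 sets up the collection form following the protocol, so the lists can pass into it. The form validation there and the conflicting-data check in section 7.8 examine data and do not correct definitions.

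A reader might try to settle the matter with the phrase "Patients who report the following diagnoses in the medical history during the follow-up period", taking it to show that ICD codes govern what is read from the chart. It cannot carry that weight: it defines a follow-up outcome, not baseline scoring.

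It is also fair to say that the study is descriptive, that section 7.7 rules out treatment comparison and names no subgroup based on these scores, and that the scores could be recomputed from the abstracted histories.

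**Conclusion.** The lists are wrong as written and should be fixed. Where they are applied, a history of stroke or systemic embolism without a G45 code costs 2 CHA2DS2-VASc points, and a prior infarct coded only I63 costs 1 HAS-BLED point. A patient aged 64 gains 1 CHA2DS2-VASc point. The misplaced haemorrhage codes shift the HAS-BLED total by 1 in some code combinations. These per-patient sizes rest only on the printed lines and labels; any cohort figure rests on an assumed prevalence.

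Stronger readings are not supported:

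- That the reported scores will certainly be wrong. The plan leaves open whether chart or code governs.
- That all 11 misplaced codes inflate HAS-BLED. A patient whose only stroke or bleeding code is one of them keeps the same total.
- That the event outcomes or the separate stroke histories are damaged. The outcomes have their own definitions. The histories come from the chart under Table 1, and Table 2 gives stroke and embolism the full code sets.
- That the apparently hepatic codes in Table 2's renal row, or the absence of I50 from the Charlson and Table 2 heart-failure lists, belong to the same fault. These lie in tables that may have lost rows in conversion, and should only be checked against the source file.

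**What to change.** 1. CHA2DS2-VASc stroke component: add I63 (except I63.6), I64, I69.3 and I74 to the G45 codes, and add I60-I62 in line with the protocol's own haemorrhagic stroke definition.
2. HAS-BLED: add I63 (except I63.6) to the stroke list and keep I64 and I69.3 there. Move the 11 haemorrhage codes to the bleeding list. State whether I60-I62 score under bleeding only or under both stroke and bleeding.
3. CHA2DS2-VASc lower age band: print 65-74 in section 7.3.1, as in the List of Abbreviations.
4. State that the chart-abstracted stroke, TIA, thromboembolism and bleeding histories feed the matching components, and which source prevails when chart and code disagree.

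The cost is small: edits to two code lists, one age band and the collection form, plus a sentence or two on sources. No new data are needed, because Table 1 already has these histories abstracted. The edits are best made before the collection form is finalised.
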